Appendix 11 Imputation Rules for Partial or Missing Dates (cont.)

	Start Date/Time	End Date/Time
Laboratory	Partially Missing Day: No imputation Month: No imputation Year: No imputation Seconds: 23 Minutes: 59 Hours: 59 Completely Missing Date: No imputation Time: 23:59:59	Partially Missing Day: No imputation Month: No imputation Year: No imputation Seconds: 23 Minutes: 59 Hours: 59 Completely Missing Date: No imputation Time: 23:59:59
Adverse Events	Partially Missing Day: If the MM-YYYY of start date is not equal to the MM-YYYY of first treatment date then set to 01-MM-YYYY. If the MM-YYYY of start date is equal to the MM-YYYY of first treatment date then if the end date is \geq date of first treatment set to max(01-MM-YYYY, date of first treatment) , otherwise if end date < date of first treatment set to 01-MM-YYYY. Month: Set to max(01-01-YYYY, date of first treatment). Year: Set to start date of first treatment. Seconds: 59 Minutes: 59 Hours: 23 Completely Missing Set to start date of first treatment. Note: For all imputations above, if the resulting imputed start date is after the end date then set start date to end date.	Partially Missing Day: Set to last day of the month, unless the outcome is death in which case impute with min(last day of month, date of death) Month: December, unless the outcome is death in which case impute with min(DD-12-YYYY, date of death) Year: If the outcome is death then impute with the date of death, otherwise no imputation. Seconds: 59 Minutes: 59 Hours: 23 Completely Missing If the outcome is death then impute with the date of death, otherwise no imputation.

**STATISTICAL ANALYSIS PLAN
48-WEEK SAFETY FOLLOW-UP**

TITLE: A RANDOMIZED, DOUBLE-BLIND, DOUBLE DUMMY, ACTIVE-COMPARATOR MULTICENTER STUDY TO EVALUATE THE EFFICACY AND SAFETY OF RITUXIMAB VERSUS MYCOPHENOLATE MOFETIL IN PATIENTS WITH PEMPHIGUS VULGARIS

PROTOCOL NUMBER: WA29330

STUDY DRUG: Rituximab

VERSION NUMBER: 1

IND NUMBER: 121595

EUDRACT NUMBER: 2014-000382-41

SPONSOR: F. Hoffmann-La Roche Ltd.

PLAN PREPARED BY: [REDACTED], Ph.D.

DATE FINAL: See electronic date stamp below.

STATISTICAL ANALYSIS PLAN APPROVAL

Date and Time(UTC)	Reason for Signing	Name
18-Oct-2019 13:14:46	Company Signatory	[REDACTED]

CONFIDENTIAL

1. BACKGROUND

Study WA29330 (PEMPHIX) aims to evaluate the efficacy and safety of rituximab (RTX) versus mycophenolate mofetil (MMF) in patients with pemphigus vulgaris (PV). PV is a rare, serious autoimmune disease characterized by blisters and erosions of the skin and mucosal areas.

Study WA29330 is an international, multicentre, randomized, double-blind, double-dummy, active-comparator, two-arm, parallel-group study, which consists of three periods: a screening period of up to 28 days; a 52-week, double-blinded, treatment period; and a 48-week safety follow up (SFU) period that begins at the time of study treatment completion or discontinuation. All patients who withdraw early from the 52-week treatment period or who complete the 52-week treatment period, must return for post-study treatment SFU assessments at 12, 24, 36, and 48 weeks after either the early withdrawal visit or study treatment completion, respectively.

A separate primary Statistical Analysis Plan (SAP) which describes the statistical methodology and data handling rules used for the 52-week treatment period was finalized before primary database freeze, the analyses completed, and Clinical Study Report (CSR) finalized. This SAP describes the timing and data handling rules to be used for the 48-week SFU period prior to final database lock.

2. ANALYSIS TIMING

The SFU analysis will be conducted when all patients have completed the 48-week SFU period or withdraw early from SFU ([Appendix 1](#)). The final CSR will include all available data up to study completion (last patient's last visit [LPLV] in SFU) or early withdrawal from SFU.

3. STATISTICAL METHODS

All analyses, summaries, and listings will be performed using SAS® software (Version 9.2 or later).

3.1 ANALYSIS POPULATIONS

The primary analysis populations are defined in the primary SAP, Section 4.1.

The rescue population (RP) includes patients who received at least one rescue therapy during the study (i.e., between Week 12 to Week 52 of the study treatment period).

The analysis populations in SFU will be the subset of patients in the primary analysis populations who entered the SFU period.

3.2 DATA-CUT FOR ANALYSES

SFU period begins at the time of study treatment completion (for patients who complete the 52-week treatment period) or discontinuation.

For each patient, start of SFU period will be earliest of the following:

- Cut-off for Week 52+1 day (i.e., Day 375+1 day)
- Date of early treatment discontinuation+1 day

Each subsequent assessment point will be assigned a study day calculated as:

date of assessment – date of first dose + 1.

For patients who had their Week 52 visit after the Week 52 cut-off date (Day 365+10 days), the Week 52 data will be included in the analysis of the SFU period.

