2.4 ANALYSIS TIMING

The primary analysis will be conducted when all patients have completed the Week 52 study visit or have withdrawn early from the study. The reporting event for the primary analysis will include data for all patients up to their Week 52 assessment visit within the treatment period, or data up to the point of withdrawal. Safety follow up (SFU) data will not be included within the primary analysis data-cut. All data up to the Week 52 study visit will form part of the Primary Week 52 Clinical Study Report (CSR).

A final reporting event and study database lock will occur after all patients complete the 48-week SFU period or withdraw early from SFU, details of which will be documented in a separate SAP and final CSR. The final CSR will include all available data up to study completion (last patient's last visit [LPLV] in SFU) or early withdrawal from SFU.

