4.5 DATA-CUT FOR ANALYSES

For each patient, the day of first dose of study treatment will be designated study day 1. Each subsequent assessment point will be assigned a study day calculated as:

date of assessment – date of first dose+1.

Data beyond the Week 52 visit will not be included in the primary Week 52 CSR. For each patient, data will be cut-off and reported up to and including the earliest of the following:

- Week 52 visit (using upper visit window of Day 364+10 days)
- Date of early withdrawal

Patients who complete the 52-week treatment period but have a missing Week 52 visit, or where the Week 52 visit falls outside the reporting cut-off will be evaluated up to study Day 365 for all analyses involving a duration or exposure element. In such analyses, any references to Week 52 throughout this SAP will imply study day 365 for these patients.

Although SFU data will not be included in data displays for the Week 52 primary reporting event, any deaths at the time of the data-cut, occurring in SFU will be highlighted in the CSR.

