3.6.1 Adverse Events

Adverse events (AEs) will be mapped and reported using the MedDRA thesaurus using the most current version at the time of analysis (version 17.1 or later). Glossaries showing the mapping of investigator verbatim terms to coded events will be produced.

AEs with observed or imputed onset date, on or after the start date of the SFU period, will be summarized and listed.

AEs will be summarized by system organ class (SOC) and preferred term (PT), and will be presented in order of descending frequency summed across the treatment arms within each SOC and PT.

Listings will show AEs reported, and highlight the telemedicine patients, the patients who received rescue therapy in the 52-week treatment period and the patients who received rituximab in the SFU period.

The following will be summarized, and/or listings produced where required:

- SAEs
- Infections
- Serious Infections
- Symptoms of Serious Infusion Related Reactions (IRRs)
- SAEs leading to withdrawal

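### As written, serious adverse events and infections in the 8–14 days after a completer's on-time Week 52 visit are tabulated in neither the Week 52 nor the safety follow-up analysis

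*SAP*

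**What the plan says.** The SAP file holds two plans: the primary (Week 52) SAP and the 48-week SFU SAP.

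**Primary SAP, end of the Week 52 data**
- Section 2.4: the reporting event covers "data for all patients up to their Week 52 assessment visit within the treatment period", and "Safety follow up (SFU) data will not be included within the primary analysis data-cut".
- Section 4.5: "Data beyond the Week 52 visit will not be included in the primary Week 52 CSR". Each patient is cut at the earlier of early withdrawal and the "Week 52 visit (using upper visit window of Day 364+10 days"). Section 4.9.1 repeats that limit for exposure.
- Section 4.6, Table 1 (the DLQI example) closes the Week 52 window at Day 375.

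**SFU SAP, start of follow-up data**
- Section 3.2 opens with a general definition: "SFU period begins at the time of study treatment completion (for patients who complete the 52-week treatment period) or discontinuation".
- The operative rule then takes the earlier of early treatment discontinuation plus one day and "Cut-off for Week 52+1 day (i.e., Day 375+1 day"). A completer has no early discontinuation date, so Day 376 applies.
- One bridging rule exists: "For patients who had their Week 52 visit after the Week 52 cut-off date (Day 365+10 days"), the Week 52 data go into the SFU analysis.
- Section 3.6.1: "AEs with observed or imputed onset date, on or after the start date of the SFU period, will be summarized and listed".

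Protocol Appendix 1 schedules the Week 52 visit on Day 364 ±3. Protocol 5.3.1 limits SFU adverse event reporting to serious events and all infections.

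**The concern.** One boundary moves with the patient and the other is fixed. The primary analysis stops at the visit, while the SFU analysis of a completer starts on Day 376 whatever the visit date. No rule covers an event with onset after an on-time visit and up to Day 375. The only bridging rule deals with late Week 52 visits.

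The data at stake are serious events and infections just after the treatment period, in a trial of a B-cell-depleting antibody against an immunosuppressant. The SFU period exists largely to report these events. The SFU SAP (section 1) says the primary analyses and their report are already final, so the follow-up analysis is the remaining place to tabulate these days.

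The upper limit itself is also written in different ways: Day 364+10 (primary SAP 4.5 and 4.9.1), Day 375 (primary SAP Table 1 and SFU SAP 3.2) and Day 365+10 (SFU SAP 3.2).

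**Working it through.** **1. The plan's own figure.** Study day = date − date of first dose + 1 (primary SAP 4.5 and 4.10.2), so there is no Day 0.
- SFU SAP: 365 + 10 = 375, so SFU starts on Day 376. This agrees with the Day 375 window end in primary SAP Table 1.
- Primary SAP 4.5 taken literally: 364 + 10 = 374, one day short.
- The two agree only if 364 is read as elapsed days: 52 × 7 + 1 + 10 = 375.

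**2. Gap if the primary cut-off is the visit.** Uncovered days = (376 − 1) − visit day = 375 − visit day.

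| Week 52 visit | Days in neither analysis | Gap | Share of the 336-day SFU (48 × 7) |
|---|---|---|---|
| Day 361 | 362–375 | 14 days | 14/336 = 4.2% |
| Day 364 | 365–375 | 11 days | 11/336 = 3.3% |
| Day 367 | 368–375 | 8 days | 8/336 = 2.4% |
| Day 374 | 375 | 1 day | 1/336 = 0.3% |
| Day 375 | none | 0 days | 0% |

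**3. Gap if the primary cut-off is a fixed day.** At Day 375: 375 − 375 = 0 days. At Day 374: 375 − 374 = 1 day.

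**4. Size.** Uncovered patient-years = completers × gap / 365.25. The documents give about 132 randomized patients but no number of completers. I assume 100 or 110, with 132 as the ceiling.

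| Visit day | 100 completers | 110 completers | 132 completers |
|---|---|---|---|
| Day 361 (14 days) | 3.8 | 4.2 | 5.1 |
| Day 364 (11 days) | 3.0 | 3.3 | 4.0 |
| Day 367 (8 days) | 2.2 | 2.4 | 2.9 |

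The documents give no serious event rate. At an assumed 10 to 40 per 100 patient-years:
- 110 completers: 2.4 × 0.10 ≈ 0.2 up to 4.2 × 0.40 ≈ 1.7 serious events.
- Across the whole table: 2.2 × 0.10 ≈ 0.2 up to 5.1 × 0.40 ≈ 2.0.

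Non-serious infections would add to this. Removing rescued completers would reduce it.

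**5. Check of the remedy.** With SFU start = visit day + 1, the uncovered days are (visit day + 1) − 1 − visit day = 0 for every on-time visit.

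**The case against.** The best counter-argument is that the primary cut-off was meant as a fixed day, and it has textual support. Primary SAP 4.5 provides for a Week 52 visit falling outside the reporting cut-off, which makes no sense if the cut-off is the visit itself. Section 4.6 maps all data up to the cut-off date, including unscheduled visits, with a window to Day 375. The SFU SAP ties its start to the Week 52 cut-off and glosses that as Day 375. The difference between 364+10 and 365+10 looks like a day-numbering slip. On this reading the two periods meet, or miss by one day.

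That reading is possible, so the 8–14 days must be stated as conditional. It does not displace the plain text, because sections 2.4 and 4.5 exclude data after the visit in so many words.

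A reader might go further and infer that these events disappear from the trial, or that only deaths are safe. The documents do not support that:
- Serious events still go to the sponsor within 24 hours (protocol 5.4), and infections are still collected.
- Deaths are listed (SFU SAP 3.6.2), and deaths in SFU known at the primary data-cut are highlighted in the Week 52 report (primary SAP 4.5).
- Safety after rescue is analysed separately (primary SAP 4.9, SFU SAP 3.2.1).
- Early discontinuers have a patient-specific SFU start.
- Pregnancies cannot be called lost. SFU SAP 3.6 reports them for the whole SFU period, which the opening sentence of 3.2 starts at treatment completion.

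SFU SAP section 2 does promise that the final report will include all available data. That states an intention, and the adverse event rule in 3.6.1 does not deliver it for these days.

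**Conclusion.** The concern stands as an inconsistency between the two plans about where one analysis period ends and the next begins. On the plain text, serious events and infections with onset in the 8–14 days after an on-time Week 52 visit are tabulated in neither analysis, mainly for non-rescued completers. If the primary cut-off was in fact applied as a fixed day, the gap is zero or one day.

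The expected effect is small: roughly 0.2 to 2 serious events, resting on assumed completer numbers (100 to 132) and assumed rates (10 to 40 per 100 patient-years), plus an unquantified number of non-serious infections. What is at issue is tabulation, not collection or surveillance. No primary or secondary efficacy test depends on it. It is worth correcting because the two safety reports together should account for every day of follow-up.

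**What to change.** In SFU SAP 3.2, define SFU start for each patient as the day after the primary data cut-off actually applied to that patient:
- the Week 52 visit date, if that visit is on or before the window end;
- the window end, if the Week 52 visit is missing or later, keeping the existing rule that late Week 52 data go into SFU;
- the early withdrawal or discontinuation date otherwise.

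The second case needs its own line. A bare visit-plus-one rule would start SFU on Day 381 for a Day 380 visit and drop the Week 52 data that section 3.2 assigns to SFU. For missing or late visits, the text should also say how the window end relates to the Day 365 convention in primary SAP 4.5, which governs duration and exposure analyses.

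State one upper limit, Day 374 or Day 375, in primary SAP 4.5, 4.9.1 and Table 1 and in SFU SAP 3.2. Since the primary report is final, the change to the primary SAP would be a note recording what was applied.

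The cost is a short rewording and one derived date, with no new data. There is a small downside. The SFU baseline date moves 14 to 8 days earlier for on-time completers if the visit was the cut-off applied. The SFU visit windows (SFU SAP 3.3, Table 1) and SFU duration (3.4) must then be re-derived. Corticosteroid exposure and flare counts over the SFU period follow the same date.

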3.2.1 Rescue Patients

Rescue patients are patients who received rescue therapy during the study (i.e., Week 12 to Week 52). There is no rescue therapy in the SFU.

The analysis of safety will be performed separately for rescue patients after the point of rescue therapy initiation.

The analysis of exploratory efficacy will be performed on the patients who haven't received rescue therapy during the 52-week treatment period, and the data for rescue patients will be excluded.

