2.3 DETERMINATION OF SAMPLE SIZE

The primary efficacy endpoint of this study is the proportion of patients (excluding TM patients) achieving a sustained complete remission, as assessed at Week 52, that has been maintained for ≥ 16 consecutive weeks during the 52-week treatment period. With use of limited data available in the literature from randomized clinical trials of MMF and investigator-initiated trials of rituximab ([Beissert et al. 2010](#)), it is estimated that approximately 40% of patients with PV receiving MMF will achieve a sustained complete remission. It is estimated that patients receiving rituximab will induce a sustained complete remission rate of 65%. On the basis of these assumptions, a total of 122 patients randomized to either the rituximab arm or the MMF arm in a 1:1 ratio (61 patients in the rituximab arm and 61 patients in the MMF arm) will yield approximately 80% power in a two-sided test at the 5% significance level. To account for the 10 TM patients excluded from the primary efficacy analysis, approximately 132 patients will be randomized in total. The sample size calculation was performed using nQuery Advisor 7 using the two-group chi-squared test of equal proportions. The primary analysis method using a Cochran-Mantel-Haenszel test adjusting for stratification factors is expected to provide at least 80% power to detect the difference in proportions.

Rituximab—F. Hoffmann-La Roche Ltd
8/Statistical Analysis Plan WA29330

No adjustment will be made for dropouts. Patients withdrawing early from the study or meeting the criteria for treatment failure (including rescue therapy) will be assessed based on available data up until the point of withdrawal or treatment failure only for the primary endpoint. Patients with missing or incomplete data where a status cannot be determined after applying relevant imputation rules will be set to non-responders.

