3.7 EXPLORATORY ANALYSES

The exploratory efficacy analysis will be performed on the mITT population as defined in primary SAP, Section 4.1.5.

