3.7.1.3 Total Number of Flares

The total number of flares occurring during the SFU period will be summarized and analyzed as described in the primary SAP, Section 4.7.2.2.

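### The follow-up SAP names the mITT population but drops every rescued patient, so its modelled flare comparison rests on a subset selected after randomisation by treatment failure

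*SAP*

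**What the plan says.** The SAP file contains a primary SAP for the 52-week treatment period and a separate SAP for the 48-week safety follow-up.

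- **Exclusion.** Follow-up SAP, Section 3.2.1 restricts exploratory efficacy to patients not rescued in the treatment period and adds that "the data for rescue patients will be excluded".
- **Named population.** Follow-up SAP, Section 3.7: "The exploratory efficacy analysis will be performed on the mITT population as defined in primary SAP, Section 4.1.5". Primary SAP, Section 4.1.5 builds mITT from ITT by removing the 10 telemedicine patients and nobody else. Follow-up SAP, Section 3.1 takes, for each primary population, those who entered follow-up. It defines a rescue population separately (at least one rescue therapy, Weeks 12 to 52) and does not subtract it.
- **Flare analysis.** Follow-up SAP, Section 3.7.1.3: "The total number of flares occurring during the SFU period will be summarized and analyzed as described in the primary SAP, Section 4.7.2.2". Primary SAP, Section 4.7.2.2 is a Poisson regression (negative binomial or zero-inflated if needed) that reports a rate ratio between arms with a 95% confidence interval and p-value. Its exposure period runs from Day 1 to the first of withdrawal, rescue or the Week 52 visit.
- **Route to rescue.** Under primary SAP, Section 4.2, patients become eligible for rescue from Week 12 by meeting treatment-failure criteria, which include steroid increases for disease activity and failure to reach disease control.
- **Earlier failures.** Protocol, Section 3.1.1 sends patients who fail before Week 12 to an early withdrawal visit and then into follow-up on standard care.

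**The concern.** Two sections of one SAP give different sets for the same analysis. A programmer working from 3.1 and 3.7 would keep rescued patients; one working from 3.2.1 would remove them.

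The choice matters because rescue is a consequence of how the patient did on randomised treatment. Removing rescued patients takes poor responders out of each arm in proportion to that arm's rescue rate. If the rates differ, the remaining groups are no longer comparable, and the arm with more rescue keeps a more favourable remainder. For flares this feeds a formal comparison with a p-value. The other follow-up efficacy outcomes (steroid use, PDAI, DLQI, Skindex-29, PGIC, CGIC) are only summarised by arm, but on the same selected set.

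**Working it through.** **1. The plan's own figure.** The only design figure is the primary power, "approximately 80% power in a two-sided test at the 5% significance level", for 40% versus 65% with "61 patients in the rituximab arm and 61 patients in the MMF arm". With pooled p = 0.525:

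power = Φ[(0.25·√61 − 1.96·√(2·0.525·0.475)) / √(0.40·0.60 + 0.65·0.35)] = Φ[(1.953 − 1.384)/0.684] = Φ(0.83) = 0.797.

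This reproduces the stated power, and the present point does not touch it. The plan gives no rescue rate, follow-up flare rate or follow-up power, so everything numerical below is illustration under stated assumptions.

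**2. Who is in and who is out under Section 3.2.1.**

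| Patient | Follow-up efficacy under 3.2.1 | Under 3.1 and 3.7 |
|---|---|---|
| No failure in the treatment period | in | in |
| Failed before Week 12, standard care in follow-up | in | in |
| Failed from Week 12, not rescued | in | in |
| Failed from Week 12, rescued | out | in |

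The rows differ only for rescued patients, and failures are treated differently according to timing and whether rescue was given.

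**3. Main illustration.** Each patient's flare rate is gamma distributed with shape 2 and mean 1. Rescue goes to the top fraction of flare rate plus normal noise with SD 0.5. There are 400,000 simulated patients. Rescue does not alter the later rate, and the true follow-up ratio (rituximab/MMF) is 1.00. The estimate after exclusion is the ratio of mean rates among non-rescued patients.

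| Rescue, rituximab vs MMF (assumed) | Ratio after exclusion |
|---|---|
| 10% vs 10% | 1.00 |
| 10% vs 15% | 1.06 |
| 10% vs 25% | 1.17 |
| 5% vs 20% | 1.19 |

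A true ratio of 0.60 scales in the same way: 0.60 × 1.17 = 0.70 and 0.60 × 1.19 = 0.71. If rescue is less closely tied to flare tendency, the shift for a 15-point gap shrinks to about 1.1 (noise SD 1) or about 1.06 (noise SD 2). Swapping the rescue rates between arms inverts the ratios.

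**4. Cross-check with two risk classes.** Let a share h of each arm flare at k times the rate of the rest, with rescue (fraction r of the arm) only among them. The mean relative rate in those kept is f(r) = [(h − r)k + (1 − h)]/(1 − r). For h = 0.4 and k = 3:

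- f(0.05) = (0.35·3 + 0.6)/0.95 = 1.737
- f(0.25) = (0.15·3 + 0.6)/0.75 = 1.400
- ratio = 1.737/1.400 = 1.24

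Over h = 0.4 or 0.6 and k = 2, 3 or 5, with 5% rescue in one arm, the ratio is 1.03–1.14, 1.08–1.37 or 1.14–1.89 for 15%, 25% or 35% in the other. It is 1.00 for 10% in both.

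In 20,000 simulated trials per setting (61 per arm, 48 weeks, h = 0.4, low-risk rate 0.4 per year, unadjusted log rate ratio with robust variance), a nominal 5% test rejected in 5.1–5.3% with everyone kept. After exclusion, with 5% rescue in one arm, it rejected in:

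| k | Rescue in the other arm | Rejection |
|---|---|---|
| 3 | 15% | 6.1% |
| 3 | 25% | 11.3% |
| 5 | 25% | 20.8% |
| 5 | 35% | 55.0% |

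**5. Letting rescue work.** Repeat step 3 with rescue multiplying later flare rates by an assumed 0.3 to 0.6, keeping everyone. Against a study-drug ratio of 1.00, the all-mITT ratio is 1.12–1.24 (5% vs 20%) or 1.11–1.22 (10% vs 25%). Keeping everyone therefore does not recover the study-drug ratio when rescue is effective.

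**The case against.** The best defence reads 3.2.1 as a specific rule narrowing the general statement in 3.7, so the set is simply mITT minus rescued patients. It carries forward primary SAP, Section 4.2, which uses rescued patients only up to rescue, and Section 4.7.2.2, where flare exposure stops at rescue. Moreover, as step 5 shows, the all-mITT analysis misses the study-drug ratio by a similar amount if rescue works. Follow-up is not a clean drug contrast in any case: patients go to standard care (Protocol, Appendix 2), and follow-up SAP, Section 3.6.1 expects some to receive rituximab. Rescued patients are reported elsewhere, for safety and study conduct.

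Much of this stands. The two sections can be reconciled, and the figures in steps 3 and 4 do not rank the two analyses if the target is the study drug alone.

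The rest does not. In the treatment period the up-to-rescue rule truncates a patient's data. In follow-up, all of a rescued patient's data come after rescue, so the same idea deletes the patient. The exposure argument proves too much, because 4.7.2.2 also ends exposure at Week 52 and so cannot be applied to follow-up as written for anyone. The exclusion does not isolate the study drug either, since early failures on standard care remain. No follow-up efficacy summary includes rescued patients. The all-mITT ratio, by contrast, compares the arms as randomised and validly estimates the randomised strategy including rescue.

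A reader might infer that the exclusion was chosen with the results in view, because follow-up SAP, Section 1 says the treatment-period analyses and report were already complete. The documents give no rationale for the rule, but nothing in them shows motive.

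**Conclusion.** The point holds as an inconsistency with a conditional statistical consequence. Sections 3.2.1 and 3.7 name different sets, and under 3.2.1 the modelled flare comparison is not protected by randomisation. It is biased if rescue differs between arms. Under the assumptions of step 3, the distortion of a true 1.00 is about 17–19% for a 15-point gap, 6% for 10% versus 15%, and none for equal rescue. Those sizes depend on assumed rescue rates, an assumed frailty, and rescue having no effect on later flares.

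A reader might go further and conclude that the follow-up comparison is certainly biased, and against rituximab. The documents do not support that: they give no rescue rates by arm, so neither a bias nor its direction is established. Nor does the point threaten the trial's main conclusions. The follow-up efficacy analyses are exploratory and outside the fixed testing sequence in primary SAP, Section 4.7. Only flares are modelled, and the primary endpoint is unaffected. This is a minor but worthwhile correction.

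**What to change.** - Align Section 3.2.1 with Sections 3.1 and 3.7 of the follow-up SAP. Make all mITT patients who entered follow-up, in their randomised arm and with rescue status flagged, the main set for the flare model and the efficacy summaries.
- Define exposure for the follow-up flare model from the start of follow-up to the last follow-up assessment, the duration already set out in follow-up SAP, Section 3.4, in place of the treatment-period definition in primary SAP, Section 4.7.2.2.
- State that this estimates the effect of the randomised strategy including rescue, and not of study drug alone.
- Show the non-rescued subset as a descriptive supplement without a p-value, with the number excluded in each arm.

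The cost is a few lines of SAP wording and re-run tables on data already collected. The price in interpretation is that the main follow-up comparison includes the effect of rescue, which is why the estimand must be stated.
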